##### 5.4 Exploratory Endpoints

- Clinical success rate as defined above, by anchor size

## 6. Statistical Considerations

### 6.1 Determination of Sample Size

Precision Analysis will be used to assess the overall proportion of success for the Q- FIX All-Suture Anchor System. Assuming a 5% lost to follow-up rate after the first year, a minimum of 90 subjects, with maximum enrollment set at 450 subjects, will be enrolled (based on the inclusion/exclusion criteria) in order to complete 84 evaluable subjects. The 90 subjects will be enrolled to allow a minimum of 28 subjects with each of the following indications to be recruited: Shoulder, Hip and Knee. Based on the results of the Byrd et al study which showed a failure rate of 1.6% in the use of the Q- FIX All-Suture Anchor System, this number of subjects is sufficient to estimate the success rate to within 11% by use of the two-sided 95% confidence interval (based on an estimate of the rate of clinical success at least 95%).

### 6.2 Randomisation

N/A.

### 6.3 Interim Analysis

Not Applicable

## 7. Statistical Analysis

### 7.1 General

Smith and Nephew Global Biostatistics Department will conduct the statistical analyses for this study. Unless otherwise stated, all significance tests from the analyses will be two-sided using the 5% significance level as the threshold of establishing statistical significance. Resulting p-values will be quoted and 95% two-sided confidence intervals will be calculated where appropriate. All p-values will be rounded to three decimal places, p=values less than 0.001 will be presented as <.0001 in all tables. Categorical variables will be summarized with frequencies (n) and percentages (%). Continuous variables and ordinal endpoints (as appropriate) will be summarized with the following summary statistics: number

#### **CONFIDENTIAL AND PROPRIETARY**

This document contains information that is confidential and proprietary to Smith & Nephew PLC and Smith & Nephew, Inc. and is intended for use only by Smith & Nephew and its manufacturer. It shall not be reproduced or copied in whole or in part, nor shall the contents be disclosed by any means without prior written permission from Smith & Nephew, nor shall anyone make any use of it that is contrary to the expressed or implied wishes of Smith & Nephew.

Statistical Analysis Plan	
Safety and Performance of Q-Fix ® All-Suture Anchor System	Number: 17-5010-11
	Version: 2.0, 23-Oct-2019
	Page: 11 of 20

of observations, mean, median, standard deviation (SD), minimum and maximum values. All analysis will be performed in SAS version 9.3 or later.

## 7.2 Analysis Populations

### Safety Population (SAF)

This includes all subjects who enroll in the study who had previously undergone arthroscopic repair using the Q-Fix™ All-Suture Anchor System i.e. subjects who only provide retrospective data.

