9.2 INCLUSION CRITERIA

Subjects will be considered qualified for enrollment if they meet the following criteria:

1. Subject has undergone arthroscopic or open soft tissue repair with Q-Fix™ All-Suture Anchor System
2. Subject was ≥ 13 of age at time of surgery

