12.2 ANALYSIS POPULATIONS

The following analysis populations will be used for this study:

- **Safety Population (SAF):** This includes all subjects who enroll in the study who had previously undergone arthroscopic or open soft tissue repair using the Q-Fix™ All-Suture Anchor System i.e. subjects who only provide retrospective data.
- **Per-Protocol Population (PP):** This includes all subjects in the Safety Population, who have no significant protocol deviations and who meet all the inclusion/exclusion criteria.

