## 2. Introduction

Post-Market Clinical Follow-up is needed to address existing clinical data and gaps on the existing Q-FIX° device and meet existing MDD/MEDDEV requirements.

The purpose of this study to assess the safety and performance of the Q-Fix° All-Suture Anchor System. This Statistical Analysis Plan (SAP) is based on protocol number 17-5010-11 version 2.0, dated 05Sep2019. This SAP presents a detailed interpretation of the study protocol by describing the statistical analyses that will be carried out for the study in greater detail than specified in the protocol. Supporting documents used to create this SAP are the Study Protocol and the Case Report Forms (CRFs). Table, Figure, and Listing (TFL) shells will accompany the SAP.

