## 3. Study Design

This is a retrospective, multi-center, case series to evaluate the 1-year safety and effectiveness of the Q-Fix° All-Suture Anchor System for arthroscopic repair when used for any of the following:

- **Shoulder:** Bankart lesion repair; superior labral tear from anterior to posterior( SLAP) lesion repair; acromio-clavicular repair; capsular shift/capsulolabral reconstruction; deltoid repair; rotator cuff repair; biceps tenodesis.
- **Hip:** Acetabular labral repair.
- **Knee:** Extra-capsular repair: medial collateral ligament (MCL), lateral collateral ligament (LCL) and posterior oblique ligament; Iliotibial band tenodesis (IBT); patellar tendon repair; vastus medialis obliquus advancement (VMO); joint capsule closure.

As the study is collecting real world data retrospectively, data may be collected on the shoulder, knee, or hip beyond the indications listed above.

Table 1 displays the information about the schedule of assessments for this study.

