### Per Protocol Population

This includes all subjects in the Safety Population who meet the inclusion/exclusion criteria and who did not encounter major deviations leading to exclusion from study. Major protocol deviations leading to removal from the PP population will include but not restricted to the following: (1) termination from the study due to non-study related reasons such as subject lost to follow-up or death.

The final assignment of a subject to the per-protocol population will be established after a review of all protocol deviations have been evaluated and deviations that would warrant exclusion of a subject from the Safety population are identified. Subjects excluded from the per-protocol population will be documented together with their reason for exclusion.

Statistical analysis will be performed using each of the subject populations as follows: (1) Analysis of the primary and secondary endpoints will be performed separately using the Per Protocol Population. (2) All safety analyses will utilize the Safety Population. (3) The Safety Population will be additionally utilized for sensitivity analysis of the primary endpoint.

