**7.11 Changes in Analysis Methods Specified in the Protocol**

N/A

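### SAP 7.2 words the Safety Population for arthroscopic repairs only, while the protocol version it implements enrols and analyses open repairs too

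*SAP*

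**What the plan says.** **Basis of the SAP.** SAP section 2 states that the plan "is based on protocol number 17-5010-11 version 2.0, dated 05Sep2019". SAP 7.11, headed "Changes in Analysis Methods Specified in the Protocol", contains only N/A.

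**Who is in the Safety Population.** SAP 7.2 takes in "all subjects who enroll in the study who had previously undergone arthroscopic repair using the" Q-Fix system. The sentence ends by glossing these as subjects whose data are purely retrospective. Protocol 12.2 has the same structure and the same gloss, but its surgical condition is having "previously undergone arthroscopic or open soft tissue repair using the" system.

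**Who is enrolled.** Protocol 9.2, criterion 1, reads "Subject has undergone arthroscopic or open soft tissue repair with" the study system. SAP section 3 describes the anchor as being "for arthroscopic repair when used for any of the following", followed by the shoulder, hip and knee uses. Open surgery is not mentioned in the SAP text available.

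**How the populations are used.** The SAP's Per Protocol definition begins "This includes all subjects in the Safety Population who meet the inclusion/exclusion criteria". It then says: "Analysis of the primary and secondary endpoints will be performed separately using the Per Protocol Population". SAP 7.2 assigns the Safety Population to all safety analyses and to the sensitivity analysis of the primary endpoint. SAP 7.6 bases the disposition table on it.

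**Intent.** Amendment #1 (protocol 23.3, item 4 of both the purpose and the rationale) added open surgery because sites were already using the anchor that way and data on both kinds were wanted. It also records that every IRB had already allowed these subjects in.

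**The concern.** The Safety Population sentence selects the subjects for almost every output, so a missing surgical category there is more than a slip in background text. The two current documents give different conditions for the same population, and the SAP does not declare a restriction.

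Taken at its word, the SAP would omit a group that the protocol deliberately enrols. Re-interventions and adverse events after open repair would be missing from the main tables. The planned sensitivity analysis could not reveal the gap. It differs from the primary analysis only in using the Safety Population instead of its Per Protocol subset, and both would lack the same subjects.

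**Working it through.** No planned figure is at issue. The check is a comparison of current texts, followed by tracing the definition through the analyses.

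**Step 1: compare the surgical condition.**

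| Place | Arthroscopic | Open |
|---|---|---|
| Protocol 9.2, inclusion criterion 1 | yes | yes |
| Protocol 12.2, Safety Population | yes | yes |
| SAP 3, study design | yes | not mentioned |
| SAP 7.2, Safety Population | yes | not mentioned |
| SAP 7.11, declared changes | none | none |

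Protocol section 12 says the SAP will account for departures from the projected analyses. A deliberate restriction should therefore appear in 7.11, and none does.

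**Step 2: trace the literal reading.** An enrolled open repair fails the surgical condition in SAP 7.2 and so is outside the Safety Population. The Per Protocol Population is a subset of it, so the subject is outside that too. The subject then drops out of:

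- the primary and secondary endpoint analyses (Per Protocol);
- the sensitivity analysis of the primary endpoint (Safety Population);
- the safety summaries (Safety Population);
- the disposition table (Safety Population).

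Two outputs are not clearly affected. The anchor-size analysis in SAP 7.9.3 is stated for all subjects. The adverse event listing in 7.9.4 names no population of its own.

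**Step 3: look for the origin.** The change table in protocol 23.3 shows arthroscopic-only wording as the v1.0 Safety Population text. That table is used here only to explain the origin; the contradiction lies between the current SAP and the current protocol. Other v2.0 changes did reach the SAP: the maximum of 450 (6.1), the endpoint for ages 13 to 21 (5.2) and the note on use beyond the listed indications (3). The amendment's statement about revising the SAP mentions only adolescents. A missed update fits all of this.

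**Step 4: ask what size can be given.** Let N be the number enrolled and f the share of open repairs. Let pA and pO be the success rates after arthroscopic and open repair.

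- Subjects lost under the literal reading: f × N.
- Rate with both kinds included: (1 − f) × pA + f × pO.
- Rate under the literal reading: pA.
- Difference: f × (pO − pA).

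The documents give neither f nor separate rates by surgical approach. They support no range for f narrower than 0 to 1, so neither the number lost nor the shift in the rate can be computed.

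**The case against.** The strongest reply is that nobody would apply the sentence that way. It opens with everyone who enrols and closes with a gloss that, in a wholly retrospective study, describes everyone enrolled. The SAP contains no filter or derivation based on surgical approach, and the documents do not show that approach is recorded. The Per Protocol definition refers to the inclusion criteria, which admit open repair. The SAP's stated basis in protocol v2.0, together with the N/A in 7.11, suggests that the protocol 12.2 definition was meant to stand. An analyst who kept open cases could cite 12.2, criterion 1 and the amendment rationale.

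Most of this stands. It makes inclusion the more natural outcome and gives an analyst recorded grounds for it. It does not remove the contradiction. Protocol 12.2 contains the same opening and the same gloss, yet the sponsor still amended its surgical wording, which suggests that the wording was treated as part of the definition.

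A reader might infer that open repairs will be excluded, or that the sponsor chose to restrict the analysis. The documents support neither: no exclusion is stated and no change is declared.

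**Conclusion.** The mismatch is certain: SAP 7.2 and SAP section 3 do not carry the open-surgery wording of the protocol version they implement, and the difference is undeclared. Its effect on the analysed subjects is uncertain. Exclusion of open repairs is possible under a literal reading but is not the likely result.

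The size cannot be computed, because no share of open cases is given. If no open repair was enrolled, nothing changes. Otherwise the literal reading would remove every one of them from the outputs listed above. A claim that the study's precision is materially damaged would need an assumed open share that the documents do not supply.

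This is a should-fix inconsistency in an analysis-population rule. It rests on the current texts of both documents and on the nesting of the Per Protocol Population in the Safety Population.

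**What to change.** Before database lock, replace the surgical condition in the SAP 7.2 Safety Population definition with that of protocol 12.2, so that it reads "previously undergone arthroscopic or open soft tissue repair using the" study system. Make the matching change in the opening sentence of SAP section 3. The Per Protocol definition needs no edit on this point, since it inherits the correction.

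The cost is two wording edits in the SAP, with no new data and no change to the planned sample size. The pooled results would then cover both kinds of surgery, as the protocol intends. The edits would not produce a separate estimate for open repair, and neither document plans one.

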### Per Protocol Population

This includes all subjects in the Safety Population who meet the inclusion/exclusion criteria and who did not encounter major deviations leading to exclusion from study. Major protocol deviations leading to removal from the PP population will include but not restricted to the following: (1) termination from the study due to non-study related reasons such as subject lost to follow-up or death.

The final assignment of a subject to the per-protocol population will be established after a review of all protocol deviations have been evaluated and deviations that would warrant exclusion of a subject from the Safety population are identified. Subjects excluded from the per-protocol population will be documented together with their reason for exclusion.

Statistical analysis will be performed using each of the subject populations as follows: (1) Analysis of the primary and secondary endpoints will be performed separately using the Per Protocol Population. (2) All safety analyses will utilize the Safety Population. (3) The Safety Population will be additionally utilized for sensitivity analysis of the primary endpoint.

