9.4 SCREENING

Participating study sites are required to document all screened subjects considered for inclusion in this study. If a subject is excluded from the study, the reasons for exclusion will be documented in the subject's source documents and noted on the Screening and Enrollment Log.

If during screening, a subject is found to have had re-intervention of the Q-Fix™ All-Suture Anchor system, the subject is still eligible to be enrolled in the study. Site staff will complete an End of Study Case Report Form (CRF) for all subjects who do not finish the study, documenting the reason for withdrawal.

CONFIDENTIAL AND PROPRIETARY

This document contains information that is confidential and proprietary to Smith & Nephew PLC and Smith & Nephew, Inc. and is intended for use only by Smith & Nephew and its manufacturer. It shall not be reproduced or copied in whole or in part, nor shall the contents be disclosed by any means without prior written permission from Smith & Nephew, nor shall anyone make any use of it that is contrary to the expressed or implied wishes of Smith & Nephew.

Study Protocol—Device	
Safety and Performance of Q-Fix™ All-Suture Anchor System	Number: 17-5010-11
	Version: 2.0 05SEP2019
	Page: Page 20 of 62

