9.7 LOST TO FOLLOW-UP

A subject will be considered lost to follow-up if he/she did not return to for follow-up per the study Investigator's standard of care.

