9.8 WITHDRAWAL

9.8.1 Conditions for Study Termination

All reasonable efforts should be made to collect 12 month postoperative data on all subjects enrolled in this study. There are multiple reasons a subject may be terminated from the study. For each case, information will be obtained on the End of Study CRF, detailing circumstances leading to the withdrawal.

9.8.1.1 *Voluntary Withdrawal*

CONFIDENTIAL AND PROPRIETARY

This document contains information that is confidential and proprietary to Smith & Nephew PLC and Smith & Nephew, Inc. and is intended for use only by Smith & Nephew and its manufacturer. It shall not be reproduced or copied in whole or in part, nor shall the contents be disclosed by any means without prior written permission from Smith & Nephew, nor shall anyone make any use of it that is contrary to the expressed or implied wishes of Smith & Nephew.

Study Protocol—Device	
Safety and Performance of Q-Fix™ All-Suture Anchor System	Number: 17-5010-11
	Version: 2.0 05SEP2019
	Page: Page 22 of 62

Study participation is voluntary and subjects may withdraw from the study without giving reason for doing so.

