## Schedule of Assessments

**Table 1. Study Procedures by Visit**

Schedule of events	Chart Review 		
	Screening	182 days post-op (±91 Days)	365 days post-op (± 91 Days )
Inclusion/Exclusion	X		
Case History Review ***	X		
Implant Status 	X	X	X
VAS	X	X	X
ROM	X	X	X
Concomitant Medications, Procedures 	*	*	*
AE Assessment	*	*	*
Serious Adverse Event (SAE) / Adverse Device Effect (ADE) / Device Deficiency (DevD)	*	*	*
End of Study/Subject disposition	*	*	*

Given the retrospective study design, data will be collected to the extent it is available.

Informed consent/waiver of informed consent from the IRB/EC must be obtained prior to retrospective data collection.

Subjects who have undergone a revision procedure of the anchor will be considered terminated from the study from the date of the revision. Study related data will not be collected following the date of the revision.

 Any concomitant medications/ procedures associated with an AE, SAE or SADE will be recorded.

\*if applicable

\*\*\* Review of subject demographics, medical history, operative, post-op, discharge, and cumulative AE's occurring since date of surgery

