## 7.3 Handling of Missing, Incomplete and Repeat Data

No imputation methods are planned for missing data in this study. Only observed data will be summarized and analyzed.

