## 7.6 Disposition of Subjects

Patient accounting will be presented as follows:

- Complete Data Per Protocol: Subjects with complete data for the primary endpoint, evaluated per protocol, in the window time frame.
- Any Data: Subjects with any follow-up data reviewed or evaluated by investigator (“all evaluated” accounting).
- Theoretically Due: Number of subjects that would have reached the beginning of the study window associated with each visit if all subjects returned.
- Not Yet Overdue: Subjects who have not yet returned visited but whose visiting window is still open.
- Deaths: Cumulative number of subjects that died during or prior to the study visit.
- Revision: Cumulative number of subjects that failed (revision) during or prior to the study visit.
- Expected Visit: Theoretical subjects minus the number of deaths and revisions.
- % Follow-up: Any Data/Expected\*100
- % Follow-up Per Protocol: Complete Data Per Protocol / Expected \*100

Additionally information on subjects discontinued from the study prematurely will be presented, with a breakdown of the reasons for discontinuation as reported in the CRF. The disposition table will be based on the population from the Safety Population. A Disposition table will also be created in order to summarize the outcomes in terms of implants.

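### The SAP 7.2 per-protocol exclusion for loss to follow-up or death has no time limit, so it can drop subjects already documented revision-free at 6 months from the primary analysis

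*SAP*

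**What the plan says.** SAP 7.2 lists what will remove a subject from the PP set, and the one item it names is "termination from the study due to non-study related reasons such as subject lost to follow-up or death". No date or visit is attached. The same section makes this single PP set the analysis set for the primary and the secondary endpoints, and adds: "The Safety Population will be additionally utilized for sensitivity analysis of the primary endpoint". Final PP assignment follows a review of deviations. SAP 7.7 says that the deviations leading to exclusion are settled before database lock.

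The passages that decide who is caught by the rule are these:

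- Protocol 9.8.1 sets the follow-up target: "All reasonable efforts should be made to collect 12 month postoperative data on all subjects enrolled in this study".
- Protocol 9.4 has site staff "complete an End of Study Case Report Form (CRF) for all subjects who do not finish the study", with the reason recorded.
- Protocol 9.7 counts a subject as "lost to follow-up if he/she did not return to for follow-up per the study" investigator's standard of care. It gives no time point.
- SAP Table 1, footnote 3: "Subjects who have undergone a revision procedure of the anchor will be considered terminated from the study from the date of the revision".
- SAP 7.3, on missing data: "Only observed data will be summarized and analyzed".
- SAP 7.6 does tie one disposition count to the visit: "Subjects with complete data for the primary endpoint, evaluated per protocol, in the window time frame".

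Protocol 12.2 defines the PP set by eligibility and absence of significant deviations. It does not name loss or death.

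**The concern.** The 6-month outcome of a subject seen revision-free in the 6-month window is known. If that subject is then recorded as lost, or dies, before the 12-month visit, the termination has a reason that SAP 7.2 names, and the subject leaves the PP set for both endpoints. A subject revised early is terminated because of the revision, which is not one of the unrelated reasons, and so remains as a failure.

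Inclusion in the 6-month rate then depends on events after 6 months and on the outcome itself: known successes can be removed and known failures cannot. The SAP does not need this rule at 6 months, since SAP 7.3 already restricts analysis to observed data. At stake is a small downward error in the primary estimate, and in the 6-month rate for ages 13 to 21. No decision rule is affected, because the study reports a rate with its confidence interval.

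**Working it through.** **The plan's own figure.** SAP 6.1 enrolls at least 90 subjects to obtain 84 evaluable (28 per joint) with 5% loss. 84/0.95 = 88.4, so 89. Per joint, 28/0.95 = 29.5, so 30, and 3 × 30 = 90. The figure reproduces. The SAP attaches this 5% to the period after the first year, so it is not a rate for loss between 6 and 12 months. No document gives such a rate.

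**Inputs.**
- N = 90 and 450 (SAP 6.1), and N = 229, the enrollment reported in Protocol 23.3 (106 + 99 + 24).
- Revised before day 273: r = 4, 11 and 22, about 5%, matching the 95% success in SAP 6.1.
- Late losses L: assumed 5% or 20% of unrevised subjects, all after a revision-free 6-month observation (L = 4, 11, 21 or 17, 44, 86).
- Exact (Clopper-Pearson) 95% intervals, as in SAP 7.9.1.

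**Formulas.** Time-linked rule: (N − r)/N. Literal rule: (N − r − L)/(N − L).

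| N | Time-linked | Literal, 5% late loss | Gap (points) | Literal, 20% late loss | Gap (points) |
|---|---|---|---|---|---|
| 90 | 86/90 = 95.56% (89.0–98.8) | 82/86 = 95.35% (88.5–98.7) | −0.21 | 69/73 = 94.52% (86.6–98.5) | −1.03 |
| 229 | 218/229 = 95.20% (91.6–97.6) | 207/218 = 94.95% (91.2–97.5) | −0.24 | 174/185 = 94.05% (89.6–97.0) | −1.14 |
| 450 | 428/450 = 95.11% (92.7–96.9) | 407/429 = 94.87% (92.3–96.8) | −0.24 | 342/364 = 93.96% (91.0–96.2) | −1.16 |

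For comparison, the interval half-widths under the time-linked rule are 4.9, 3.0 and 2.1 points.

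If about half of the losses come before any 6-month observation, both rules drop those subjects. The gap shrinks to about −0.1 point at 5% (N = 90: 82/86 against 84/88 = 95.45%) and about −0.6 at 20%. For one joint with N = 30, 2 revised and 1 late loss, 27/29 = 93.1% compares with 28/30 = 93.3%.

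**Does a time-linked rule have its own error?** SAP 7.4.1 counts revisions up to day 273, but the 6-month window in SAP 7.4 opens at day 91. An unrevised subject last seen on day 91 would count as a success with part of the risk period unobserved. Assume a true 95% revision-free at day 273 and a constant revision rate, so that S(d) = 0.95^(d/273), giving S(91) = 0.983 and S(182) = 0.966. Let a share s of charts end at day d.

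- Time-linked: 0.95(1 − s) + s·S(d)
- Literal, if those subjects are recorded as lost: 0.95(1 − s) / [(1 − s) + s(1 − S(d))]

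| Charts end at | s | Literal, error (points) | Time-linked, error (points) |
|---|---|---|---|
| day 91 | 5% | −0.08 | +0.17 |
| day 91 | 20% | −0.40 | +0.66 |
| day 182 | 5% | −0.17 | +0.08 |
| day 182 | 20% | −0.79 | +0.33 |
| day 273 | 5% | −0.25 | 0 |
| day 273 | 20% | −1.17 | 0 |

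The time-linked rule has the smaller error for subjects last seen at day 182 or later, and the larger error for those last seen at the opening of the window.

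**12 months.** SAP 7.4.2 counts only revisions from day 273 to day 456. If early-revised subjects stay in the 12-month denominator under that definition, then with 4 early revisions and none later (assumed) the rate reads 90/90 instead of 86/90.

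**The case against.** The best case for the plan has four parts.

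*Loss may rarely be recorded.* Protocol 9.7 judges loss against each site's standard of care, and Protocol 9.3 requires only that a subject be more than 6 months post-operative. Where routine follow-up ends near 6 months, absent 12-month data need not be a loss. This stands. A reader might infer that everyone without 12-month data is dropped; the documents do not say so. Death after 6 months is still caught, but no rate is given.

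*The deviation review can repair it.* SAP 7.2 and 7.7 leave PP exclusions open until database lock, so a time limit could be added then. That also stands, but it permits a repair without making one: loss and death are already named as removals.

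*The Safety Population analysis restores these subjects.* It does for the primary endpoint, though it also brings back ineligible subjects, so it does not isolate the effect. For ages 13 to 21, SAP 7.2 names this sensitivity analysis for the primary endpoint only, whereas SAP 7.9.2 and Protocol 12.3.2 carry over the primary analysis and can be read to include it.

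*The remedy is not free of error.* This is correct for subjects last seen early in the window, and that error favors the device. It has to be disclosed.

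**Conclusion.** The point holds as a minor wording defect. The text gives the exclusion no time limit, and nothing elsewhere supplies one. Taken literally, it can remove known 6-month successes and never known failures. The size given above rests on about 5% revised, losses only among the unrevised, and assumed late-loss rates of 5% and 20%.

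Two stronger readings are not supported. A reader might suspect that the exclusion flatters the device; by itself it works the other way. A reader might also take the planned 5% as the documented loss between 6 and 12 months; SAP 6.1 places it after the first year. Confidence is high that the time limit is missing, and lower on how many subjects it would affect.

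**What to change.** Before database lock, state in SAP 7.2:

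1. Loss or death removes a subject from an endpoint's PP analysis only if it occurred before that subject's status for that endpoint was observed. Later loss or death does not remove the subject from the 6-month analysis.
2. Subjects revised before the cut-off stay in as failures.
3. Unrevised subjects last seen inside the 6-month window (days 91 to 272) are kept as observed, in line with SAP 7.3 and 7.4. The report discloses the small upward error that arises because revisions count to day 273.
4. The rule is applied at 12 months only after it is reconciled with SAP 7.4.2, so that revisions before day 273 do not enter the 12-month denominator as successes.

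The 6-month change costs a sentence or two and a PP flag per endpoint; SAP 7.6 already plans per-visit counts. The 12-month step also needs an edit to SAP 7.4.2. One small downward effect remains, because unrevised subjects with no 6-month observation still drop out (84/88 = 95.45% against 86/90 = 95.56%). Requiring unrevised subjects to be followed to day 273 would be worse: if half of the 86 unrevised were last seen on days 91 to 272, the rate would read 43/47 = 91.5%.

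A Kaplan-Meier revision-free estimate, censored at last contact or death, is an optional and separate addition. It needs a last-contact date, which the documents do not show to be collected, and assumes non-informative censoring.

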10.3.4 Subject Attrition

Subject attrition for the sample size has been accounted for in the estimate of the Confidence Interval so as to validate the analysis and most efficiently use the available subjects.

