#### 7.4.1 Derived Data for the Primary Endpoint

The final count of re-interventions for the 6 month post-operative time point will be defined as any revision that occurred before the end of the 6 Month window (273 days),

i.e. if (Date of Revision – Date of Surgery) < 273 days,

where the Date of Revision is obtained from the Implant Revision CRF and the Surgery Date is obtained from the Operative Data CRF.

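### The only planned sensitivity analysis of the primary endpoint does not test loss to follow-up: lost or dead subjects without a recorded revision can leave the success rate unchanged or raise it, never lower it

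*SAP*

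**What the plan says.** - **Primary population.** SAP 7.2 limits PP to subjects "who meet the inclusion/exclusion criteria and who did not encounter major deviations leading to exclusion from study". The list of exclusions is open ("Major protocol deviations leading to removal from the PP population will include but not restricted to the following"), and the one example given is "termination from the study due to non-study related reasons such as subject lost to follow-up or death". SAP 7.7 leaves the remaining exclusions to be settled before database lock.
- **Sensitivity analysis.** SAP 7.2, item (3): "The Safety Population will be additionally utilized for sensitivity analysis of the primary endpoint". SAP 7.9.1 and Protocol 12.3.1 say the same. SAF is defined in SAP 7.2: "This includes all subjects who enroll in the study who had previously undergone arthroscopic repair". (Protocol 12.2 also names open repair; that difference is not at issue here.)
- **Failure.** SAP 7.4.1 counts "any revision that occurred before the end of the 6 Month window (273 days"), using the date on the revision form.
- **Missing data.** SAP 7.3: "No imputation methods are planned for missing data in this study. Only observed data will be summarized and analyzed".
- **Planning figures.** SAP 6.1 and Protocol 13 assume 5% loss, 95% success, and 90 enrolled to give 84 evaluable, 28 per joint. SAP 6.1 caps enrolment at 450.

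Neither document plans a worst-case, tipping-point or censored time-to-revision analysis, and SAP 7.11 records no change of method.

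**The concern.** This is a chart review that takes whatever data exist. Under Protocol 9.7 a subject is lost when he or she did not return under the investigator's usual care. A revision done at another hospital need not appear in the site's chart. Whether that happens often is not known from the documents, but the design cannot exclude it, and Protocol 9.5 expects lost and deceased subjects to be enrolled under a consent waiver.

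Planned loss (5%) is as large as the planned failure rate (5%), so the unobserved subjects could matter as much as the observed failures. If PP and SAF agree, a reader of the report will take this as evidence that loss did no harm. For the subjects whose outcome is unknown, the comparison gives no such evidence.

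**Working it through.** **1. The plan's own figure.** With 5% loss, 84/0.95 = 88.4, so 89 subjects. Per joint, 28/0.95 = 29.5, so 30, and 3 × 30 = 90. The stated 90 is reproduced.

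**2. What re-admission does.** Let PP have n subjects and s successes. SAF adds r subjects, of whom f have a recorded revision before day 273.

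- Added subjects without a revision counted as successes: SAF = (s + r − f)/(n + r).
- Only observed outcomes used, and none of the r observed: SAF = s/n.

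For lost or dead subjects without a recorded revision, f = 0. The rate then becomes (s + r)/(n + r), which is at least s/n, or stays at s/n. The SAP does not say which applies.

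**3. Numbers.** The counts of lost subjects and revisions are assumptions chosen near the planning figures. Intervals are Clopper-Pearson 95%, the method in SAP 7.9.1. The worst case, which is not in the plan, is s/(n + r).

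| Assumed | PP | SAF, observed only | SAF, counted as successes | Worst case |
|---|---|---|---|---|
| 90 enrolled, 6 without status, 4 revisions | 80/84 = 95.2% (88.3–98.7) | 80/84 = 95.2% | 86/90 = 95.6% (89.0–98.8) | 80/90 = 88.9% (80.5–94.5) |
| 90 enrolled, 5 without status, 4 revisions | 81/85 = 95.3% (88.4–98.7) | 81/85 = 95.3% | 86/90 = 95.6% (89.0–98.8) | 81/90 = 90.0% (81.9–95.3) |
| 450 enrolled, 23 without status, 21 revisions | 406/427 = 95.1% (92.6–96.9) | 406/427 = 95.1% | 429/450 = 95.3% | 406/450 = 90.2% (87.1–92.8) |

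The gap between PP and worst case is 6.3, 5.3 and 4.9 points. In the first row the lower limit falls by 7.7 points.

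**4. Per joint.** Assuming 30 enrolled, 2 without status and 1 revision, PP is 27/28 = 96.4% and the worst case 27/30 = 90.0% (73.5–97.9).

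**5. Larger losses, 450 enrolled, about 5% failures in PP.**

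- 10% loss: PP 385/405 = 95.1%, SAF with the lost as successes 430/450 = 95.6%, worst case 385/450 = 85.6%.
- 20% loss: PP 342/360 = 95.0%, SAF 432/450 = 96.0%, worst case 342/450 = 76.0%.

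As loss grows, SAF on this reading moves up while the worst case falls.

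**6. SAF as a whole.** SAF also re-admits ineligible subjects and other major deviators, whose recorded revisions count (f > 0). Take six re-admitted, with those not revised counted as successes. One revision gives 85/90 = 94.4% and two give 84/90 = 93.3%, both below PP at 95.2%. On this counting, SAF falls below PP whenever the failure share among the re-admitted exceeds that in PP (4/84 = 4.8%).

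**The case against.** A reader might infer that the SAF analysis as a whole can only confirm or raise the primary rate. The documents do not support that: step 6 shows it can fall, because PP excludes more than lost and dead subjects. SAF therefore retains some value as a check on the other exclusions.

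Nor is failure impossible for every lost or dead subject. SAP 7.4.1 sets no condition on disposition, so a recorded early revision in a subject coded as lost or dead counts in SAF. The footnote to SAP Table 1, which ends participation at revision, makes this uncommon but does not rule it out. Likewise, a subject with six-month status who is lost later may leave PP, and re-admission then restores a real outcome.

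The figure 86/90 is not the plan as written. The observed-data sentence in SAP 7.3 favours 80/84, and neither reading is settled.

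It is also tempting to call Protocol 10.3.4 wrong where it says "Subject attrition for the sample size has been accounted for in the estimate of the Confidence Interval". That does not stand. The planned precision is stated for the numbers after attrition, 84 evaluable and 28 per joint. The stated 11% is close to the exact half-width at n = 28 (11.3 points at 26/28), so attrition did enter the planned interval.

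Finally, SAP 7.6 tabulates follow-up, deaths, revisions and reasons for discontinuation, and SAP 7.2 documents each PP exclusion. In a descriptive series with no performance goal, a careful reader could approximate the bound. That lessens the harm, but those tables do not feed into the endpoint, and the report would still present SAF as its sensitivity analysis. Protocol 23.3 records 106 + 99 + 24 = 229 subjects already enrolled, so the rows for 90 illustrate the planning minimum and not the expected study.

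**Conclusion.** The point holds in a limited form. For lost or dead subjects without a recorded revision, the SAF analysis can only leave the success rate unchanged or raise it, so nothing planned tests whether loss to follow-up hides failures. The SAP is also silent on whether such subjects are successes or leave the denominator.

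Under the assumed counts near the planning loss, the unexamined margin is about 5 to 6 points on the overall rate, and a sample of 450 does not remove it. It widens with loss: 9.5 points at 10% (95.1 − 85.6) and 19.0 points at 20% (95.0 − 76.0). These are distances to a bound and not estimates of bias. The documents give only 5% loss, 95% success and 90 to 450 subjects; the true counts will differ.

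The primary analysis can stay as planned. What should change is its sensitivity analysis.

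**What to change.** In SAP 7.2, item (3), and SAP 7.9.1:

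1. State how a subject without a recorded revision and without follow-up status is counted in SAF: as a success, or out of the denominator.
2. Add a worst-case analysis in SAF, labelled as a bound and shown beside PP and SAF, overall and per joint. A subject with no recorded re-intervention and no documented follow-up status in or after the visit window (182 ± 91 days; 365 ± 91 days for 12 months) counts as a failure.

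Tying the rule to the window matters. A cut-off at day 182 or 365 would fail subjects seen intact inside the window, such as on day 170. The price is that a subject last seen early in the window counts as a success, so the bound covers missing status and not unrecorded revisions later in the window.

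The work is one added row per table and a few sentences of text. It needs documented status for each subject; Protocol 11.1.3 makes the six-month implant status form conditional, so the SAP should name which chart entries count as status. The downside is that a deliberately pessimistic figure appears in the report, hence the label. No change to Protocol 10.3.4 is needed.
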